Overall, the current study tests the effectiveness of a relatively low-cost intervention – a documentary promoting a plant-based diet – to reduce healthcare costs and improve health outcomes. This study will also test whether the use of commitment and prevention nudges can encourage more participants to watch the documentary and make lifestyle changes. The findings from this study will help researchers, hospital administrators, and health insurance companies design economical, evidence-supported programs that can improve people's health.

PROCEDURES

Research Design

We will use an experimental study with a factorial design (14 groups: 1 control, 1 letter only, 3 methods of documentary distribution x 4 behavioral nudges; see Detailed Study Procedures). We will also gather outcome data from five years before the intervention to two years after the intervention in order to allow pre-intervention and post-intervention analysis (which includes a primary analysis to be conducted one year after the intervention and a follow-up analysis the following year).

Study Population

Target Population and Inclusion/Exclusion Criteria. We will include Geisinger Health Plan (GHP) policy holders who are aged 18 and older. Participants should meet the following criteria:

- Has two out of the three following medical conditions:
 - Body mass index over 30
 - Diagnosis of type 2 diabetes (specifically, with at least one medication)
 - Diagnosis of cardiovascular disease
- Has health insurance through Geisinger Health Plan (is an active member with a full 12-month enrollment in the previous year) under one of the following categories:
 - Medicare with required primary care provider
 - Medicaid
 - Individual policy under the Affordable Care Act
- Has visited their primary care provider in the past 12 months
- Is not institutionalized
- Does not have cancer, cirrhosis, renal failure, dementia, or active psychosis
- Is not in the same household (spouse or adult child sharing the same address) as another selected participant

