households (see Participant Enrollment) to be enrolled in the study and randomly assign them to the 14 experimental groups. They will then give mailing information (names and addresses) to the Geisinger mailroom, who will address and mail the study materials. No recruitment or advertisement materials will be used. Our first contact with any households assigned to receive the intervention will be through the mailed study materials. If a household has multiple members, any materials will be addressed to all members of the household.

Detailed Study Procedures. Households will be randomly assigned to one of 14 experimental groups:

- Control group (1): 6,200 households will not be contacted, but their insurance and health data will be examined. This number is an estimate of the remainder of eligible participants who were not selected for other experimental groups. We plan to analyze the data of all remaining participants, as this increases statistical power for analysis without any additional cost in sending materials.
- Letter group (2): 2,200 households will receive a letter promoting a plant-based diet. This letter will feature a personal testimonial about the benefits of this diet (see attached document, Letter Versions).
- Groups 3-14 (550 households each) will receive a letter promoting a plant-based diet and the Forks Over Knives documentary. All of these households will be given a form and online link where they may choose to order a book that has more information on plant-based diets as well as a number of recipes. The groups will vary based on the method of delivering the documentary and the presence or absence of behavioral nudges in the letter. All possible combinations total to 12 groups.
 - Method of delivering the documentary
 - Online link
 - DVD
 - Online link and DVD
 - Behavioral nudge in the letter (see attached document, Letter Versions)
 - No nudge: There are no behavioral nudges included in the letter.
 - Commitment nudge: At the end of the letter promoting a plant-based diet, participants will be asked to write dates and personal signatures committing to watching the documentary. They will be asked to mail back this written commitment.
 - Prevention nudge: As part of the letter promoting a plant-based diet, one paragraph will describe the risks of not taking action. This phrasing reframes the status quo as contributing to future loss (e.g., costs of medication and operations).

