## Statistical Analysis Plan

### Project Status

All interventions have been launched and data collection is ongoing. The time period for the primary outcomes (1 year pre-intervention, 1 year post-intervention) has already elapsed, and the analysis will focus on this time period. The data have not been examined as of the time this document has been posted.

Due to delays in pulling claims-level data from the Geisinger Health Plan, we currently do not have access to 3 of the 6 primary outcomes: (1) change in number of visits, (2) change in number of prescriptions, and (3) change in number of unique prescribed medications. The plans outlined below will still be followed for these outcomes if we are later able to acquire these data. The key primary outcome – change in medical cost – was collected, as were the other primary and secondary outcomes.

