### Planned Analyses

We currently have 7 primary and 6 secondary outcome variables, with timeframes for analysis relative to the intervention date outlined below.

Outcome	Desired Level	Primary Analysis	Secondary Analysis 1	Secondary Analysis 2
Medical Cost	Lower	1 year pre, 1 year post		5 years pre, 2 years post
Visits*	Lower			
Number of Prescriptions*	Lower			
Number of Unique Prescribed Medication*	Lower			
Body Mass Index	Between 18.5 to 25			
Systolic Blood Pressure	< 120 mmHG			
Diastolic Blood Pressure	< 80 mmHG			
Triglyceride Level	< 150 mg/dl	1 year pre, 1 year post		
Low-density Lipoprotein (LDL) Level	< 100mg/dl			
High-density Lipoprotein (HLD) Level	< 60 mg/dl			
LDL/HDL Ratio	< 3 for men, < 2 for women			
Hemoglobin A1c (hba1c)	< 5.7%			
Depressed Mood and Anhedonia (PHQ-2)	Lower			

\* Data currently unavailable

For clarity in this plan, the different conditions (and planned sample sizes) of the study are presented below. Passive control participants who are missing all outcome data and all other participants who returned mail (e.g., wrong address; did not accept mail) will be excluded from the analysis.

Passive Control	Active Control (Letter with no Video)	Letter with Video			
		Link	DVD	DVD + Link	
2200	2200	550	550	550	Letter Only
		550	550	550	Commitment Nudge
		550	550	550	Prevention Nudge
		550	550	550	Commitment + Prevention
2200	2200	2200	2200	2200	

The overall hypothesis for this project is that the experimental conditions (e.g., participants who received Forks Over Knives materials; shaded yellow in the figure above) should have better outcomes compared with those in the control conditions, one year after the intervention. All outcomes are hypothesized to shift in the direction of the desired levels (i.e., lower costs, better health). Among the primary outcomes, cost is of greatest interest and importance, as it encompasses multiple other outcomes.

### Primary Analysis and Secondary Analysis 1

As we are interested in the change in each outcome between 1 year pre-intervention and 1 year post-intervention, mixed-effects regression models will be used for continuous outcomes, using a log-link function and negative binomial distribution for outcomes involving highly positively skewed count or count-related data: costs, visits, number of prescriptions, and number of unique medications. A mixed-effects logistic regression will be used for binary outcomes.

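### The SAP targets pre-to-post change without stating baseline adjustment or a common baseline mean; on the usual reading this gives up precision that the pre-year data could supply

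*SAP*

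**What the plan says.** In the SAP, the section Primary Analysis and Secondary Analysis 1 opens with the modelling statement: "As we are interested in the change in each outcome between 1 year pre-intervention and 1 year post-intervention, mixed-effects regression models will be used". Regression for cost, visits and the two prescription outcomes is planned "using a log-link function and negative binomial distribution for outcomes involving highly positively skewed count or count-related data"; binary outcomes get mixed-effects logistic regression. Questions 1 to 3 then list which groups are compared with which reference group. Nowhere does the SAP give the fixed effects, the random effects, a group-by-time term, or the role of the pre-intervention value.

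The SAP's Project Status section uses the same language of change. It says "The key primary outcome – change in medical cost – was collected", and lists among the outcomes not yet available the "change in number of visits".

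On earlier data, the Protocol (Research Design) says "We will also gather outcome data from five years before the intervention to two years after the intervention". In the SAP's outcome table the primary cost analysis uses one year before and one year after. The longer window, "5 years pre, 2 years post", is assigned to Secondary Analysis 2. Eligibility in the Protocol requires only that a participant "is an active member with a full 12-month enrollment in the previous year".

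Allocation is random: "Households will be randomly assigned to one of 14 experimental groups" (Protocol, Detailed Study Procedures).

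**The concern.** Randomisation makes the arms' pre-intervention means equal in expectation. A model that estimates a separate baseline mean for each arm and subtracts it is therefore correcting a difference that is only chance, and it carries the noise of that correction into the effect estimate. Conditioning on the pre-year value removes only the part of the baseline that predicts the outcome.

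Precision matters in this trial. Everyone mailed is analysed whether or not they open the letter (Protocol, Participant Withdrawal), so any effect among those who engage is diluted. The power calculation rested on people who did or did not request a book (Protocol, Data Analysis/Statistical Considerations), not on the randomised contrast. The SAP's own overall hypothesis concerns outcomes one year after the intervention, and a baseline-adjusted one-year difference addresses that directly.

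**Working it through.** **Plan's own figure.** The only stated sample-size figure is a minimum of 400 households. It cannot be reproduced, because alpha, power, SD and whether it is per group or in total are not given. It also contains no pre-post correlation, so it does not settle the present question.

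**Inputs.**
- One pre-year and one post-year, randomised arms: from the documents.
- Planned sample of 5 x 2,200 = 11,000: SAP condition table.
- Pre-post correlation rho: not in the documents. Assumed 0.3 to 0.7, with 0.9 shown as well.
- Equal variances, linear (or log) scale, complete data: assumed.

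**Formulas.** The variance of the arm contrast is given per unit of outcome variance; the factor for arm size is common to all and cancels.
- Post-year only: 1
- Change (free arm means at both times, arm-by-time test): 2(1 - rho)
- Pre-year value adjusted, or common baseline mean: 1 - rho^2
- Ratio of change to adjusted: 2(1 - rho)/(1 - rho^2) = 2/(1 + rho)
- Share of the sample lost: 1 - (1 + rho)/2 = (1 - rho)/2

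| rho | Change | Adjusted | Ratio | Extra participants needed | Share lost | 11,000 act like |
|---|---|---|---|---|---|---|
| 0.3 | 1.40 | 0.91 | 1.54 | 54% | 35% | 7,150 |
| 0.5 | 1.00 | 0.75 | 1.33 | 33% | 25% | 8,250 |
| 0.7 | 0.60 | 0.51 | 1.18 | 18% | 15% | 9,350 |
| 0.9 | 0.20 | 0.19 | 1.05 | 5% | 5% | 10,450 |

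The standard error is larger by the square root of the ratio: about 24%, 15%, 8% and 3%. The ratio exceeds 1 for every rho below 1, so the direction does not depend on the assumed value. Below rho 0.5 the change variance exceeds 1, so the change analysis is then less precise than ignoring the pre-year altogether.

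**Earlier cost years.** Two correlation structures bound the plausible gain from adjusting for five pre-years.
- Equal correlations between all years: the residual variance is 1 - 5rho^2/(1 + 4rho), which is 0.795, 0.583 and 0.355 at rho 0.3, 0.5 and 0.7. Against the one-pre-year change analysis the ratios are 1.40/0.795 = 1.76, 1.00/0.583 = 1.71 and 0.60/0.355 = 1.69.
- AR(1) correlations: given the most recent pre-year, the four earlier years carry no further information. The residual stays at 1 - rho^2 and the ratios stay at 1.54, 1.33 and 1.18.

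**The case against.** The strongest reply is that the criticised model is not in the SAP. Only mixed-effects regression is named, and a mixed model with one common baseline mean fits that wording too. If that was intended, the one-pre-year loss is zero. This stands as a caution: free arm baselines are the likely reading, not a certain one. It does not remove the point, because nothing in the SAP specifies the more precise model.

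A second reply is that a difference in change is unbiased under randomisation, and that no rho, cost SD or alpha is given to show that a conclusion would alter. That is correct. The point concerns efficiency only.

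A third reply is that the SAP's analysis set is not the groups as randomised. Passive controls are excluded if they lack all outcome data, while other participants are excluded for returned mail. With such a set, free arm baselines could absorb some selection imbalance, and a common baseline mean is no longer guaranteed. This also stands, and it conditions the fix.

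Fourth, the formulas are exact only for linear models with complete data. Under the negative binomial and logistic models they are a guide to size.

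A reader might also infer that the trial holds five complete pre-years of cost and discards four of them. The documents do not show this. Five years are planned, they are assigned to Secondary Analysis 2, and only 12 months of prior enrolment is assured.

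**Conclusion.** The point holds as one about precision. The SAP makes pre-to-post change its target and specifies neither adjustment for the pre-intervention value nor a common baseline mean. On the usual reading, and at an assumed rho of 0.3 to 0.7, the change analysis needs about 54% to 18% more participants than an adjusted analysis, equivalent to losing 35% to 15% of the sample. At rho 0.9 the figure is about 5% more. These sizes rest on the assumed rho, a linear scale, equal variances, complete data and comparison of the groups as randomised.

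Two stronger readings should be avoided. The 18% to 54% is the extra sample needed; it is not the share of the sample wasted. It also includes nothing for the earlier cost years, whose added gain runs from none (AR(1)) to a total variance ratio of about 1.7 (equal correlations).

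The change is worth making because it uses data the primary analysis already requires, and because the SAP says that the data had not been examined when it was posted.

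**What to change.** Write the primary model out in full. Preferred form: keep the pre and post rows and give all arms one common pre-intervention mean, with fixed effects for time and for arm in the post period and no arm term at baseline. The contrasts under Questions 1 to 3 are then read from the post-period arm terms. Apply it to the groups as randomised. This form keeps participants whose pre value is missing.

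Alternative: model the post-year value with the pre-year value as a covariate, using log(1 + pre-year value) for the log-link outcomes, and state how missing pre values are handled, since otherwise those participants drop out. The two forms are similar but not identical for non-linear models, so the SAP should name one as primary.

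For cost, earlier pre-years may be added as covariates where available, with an indicator for years not enrolled. No particular gain should be counted on.

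Cost: SAP wording, with the same data and the same class of model. The effect would be reported as a baseline-adjusted one-year difference rather than a difference in change. The common-baseline assumption also requires the as-randomised groups in place of the SAP's arm-specific exclusions, which is a real change to the analysis set and should be made openly, before the outcome data are examined.

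### The negative binomial model planned for unique medications may overstate the standard error if counts are stable from year to year; participant-clustered robust standard errors would remove the risk

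*SAP*

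**What the plan says.** The SAP (Planned Analyses, Primary Analysis and Secondary Analysis 1) targets the "change in each outcome between 1 year pre-intervention and 1 year post-intervention", so each participant contributes two values. The model class is mixed-effects regression. For the skewed outcomes the SAP adds a distribution and a link, "using a log-link function and negative binomial distribution for outcomes involving highly positively skewed count or count-related data", and the outcomes that it places in this class are "costs, visits, number of prescriptions, and number of unique medications".

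The Project Status section names "change in number of unique prescribed medications" among the primary outcomes. It says that these data are not currently available, and that the plan will be applied to them if they are obtained. It also says that no data had been examined when the SAP was posted.

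Neither document gives the random-effects structure, the type of standard error, a dispersion check, or an alternative for counts that vary less than the model allows. The protocol (Data Analysis/Statistical Considerations) refers only to general linear models, regression, and non-parametric models for non-normal insurance data.

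**The concern.** The SAP chooses the negative binomial because the outcomes are skewed. Skew describes how people differ from one another. The precision of a pre-post contrast depends on how much the same person varies between years. A random intercept absorbs the differences between people, and the negative binomial then describes what is left. What is left must have variance at least equal to the mean.

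The number of distinct medications is the listed count most likely to break that condition, because a drug continued through both years counts once in each. The population makes this plausible. Participants need two of three conditions (BMI over 30, type 2 diabetes, cardiovascular disease), and the diabetes criterion reads "Diagnosis of type 2 diabetes (specifically, with at least one medication". If much of the list carries over, the fitted dispersion can only move to its Poisson limit, and the model-based standard error stays too wide. A real fall in medications could then be reported as no effect, and a reader could not tell whether the intervention or the model was responsible.

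**Working it through.** **Inputs from the documents.** Log-link negative binomial mixed model; one year before and one year after; SAP planned sizes of 2,200 passive control, 2,200 active control and 12 × 550 = 6,600 with video. The protocol's only power figure, a minimum of 400 households, concerns insurance claims by book request, so there is no planned figure for medications to reproduce.

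**Assumptions.** Participant random intercept, group-by-time term, model-based standard errors, two-sided 5% test. The mean, variance and pre-post correlation r of unique medications are not in the documents, so a range is shown.

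**Step 1, the floor.** Given the person, the negative binomial variance is μ + μ²/θ, which is at least μ. The model's variance for the pre-post difference is therefore at least 2 × mean. The actual variance is 2 × variance × (1 - r). The floor binds when variance × (1 - r) < mean, that is, when r > 1 - mean/variance. A random slope only adds variance, so it does not help.

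**Step 2, inflation.** Above the threshold, the ratio of model to true standard error is k = sqrt(mean / [variance × (1 - r)]). Below it, k = 1.

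**Step 3, power and size.** A contrast with 80% true power has expected z = 1.96 + 0.84 = 2.80. With inflation k it is declared significant only beyond 1.96k, so power is about Φ(2.80 - 1.96k) and the actual two-sided size is 2 × [1 - Φ(1.96k)].

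**Step 4, numbers at an assumed mean of 9.**

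| Variance | Threshold r | k at r = 0.80 (power) | k at r = 0.85 (power) | k at r = 0.90 (power) |
|---|---|---|---|---|
| 25 | 1 - 9/25 = 0.64 | 1.34 (57%) | 1.55 (41%) | 1.90 (18%) |
| 36 | 1 - 9/36 = 0.75 | 1.12 (73%) | 1.29 (61%) | 1.58 (38%) |
| 49 | 1 - 9/49 = 0.82 | 1.00 (80%) | 1.11 (74%) | 1.36 (56%) |

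For example, at variance 25 and r = 0.85, k = sqrt(9 / [25 × 0.15]) = sqrt(2.4) = 1.55 and power is Φ(2.80 - 3.04) = 41%. At r = 0.85 the nominal 5% test runs at about 0.2%, 1.1% and 3.0% for the three variances.

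**Step 5, simulation of the fitted model.** Random-intercept negative binomial by maximum likelihood, 2,200 against 2,200, assumed mean 8 and SD about 5, 150 replicates per scenario. The threshold is 1 - 8/25 = 0.68. The comparison is a participant-clustered robust standard error for the same log ratio. Where two ratios are shown, they come from the runs without and with an effect.

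| r | Formula k | Simulated model SE / empirical SD | Null rejection, model-based | Power, model-based | Power, robust |
|---|---|---|---|---|---|
| 0.68 | 1.00 | 1.05, 1.11 | 0.033 | 0.79 | 0.81 |
| 0.84 | 1.41 | 1.36 | 0.013 | 0.60 | 0.84 |
| 0.90 | 1.79 | 1.85, 1.77 | 0.000 | 0.12 | 0.71 |
| 0.95 | 2.53 | 2.52, 2.42 | 0.000 | 0.01 | 0.77 |

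The model-based standard error stays near 0.015 in every row. That is the Poisson floor for this contrast: sqrt(4 / [8 × 2,200]) = 0.0151. At r = 0.68 the robust and model-based standard errors coincide (0.0151 and about 0.0152), so the excess over 1.00 in that row is simulation error, about 6% on the ratio. Null rejection with the robust standard error ranged from 0.03 to 0.07. Simulation error on power is up to 4 percentage points.

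**The case against.** A reader might infer that the standard error will be too large and that real effects will be missed. The documents do not support that. They give no mean, variance or year-to-year correlation for medications, and the data were not in hand. The threshold depends on the variance as much as on r. The SAP calls these outcomes highly skewed, and a larger variance moves the threshold up: at mean 9 and variance 49 there is no loss at r = 0.80 and only a modest one at 0.85. The eligibility criteria make chronic medication plausible but say nothing about how much of it is retained, and a person can qualify on BMI and cardiovascular disease without diabetes. A simulation that builds in high retention confirms the algebra, not that this population is in the affected region. All of this stands.

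A reader might also infer that the SAP commits to model-based standard errors. It names no type. Robust errors are compatible with its text and would remove the problem. That stands too, though a named likelihood model with nothing further said would ordinarily be reported with its model-based errors.

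Nor can one infer false positives or damage to the main result. The error lowers the type I rate, it arises only if these data are obtained, and the SAP says that "Among the primary outcomes, cost is of greatest interest and importance".

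What survives is narrower. The choice of standard error is open, one option fails in a plausible setting, and the other does not.

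**Conclusion.** The concern holds as a conditional one. If model-based standard errors are used, and if the pre-post correlation of unique medications exceeds about 1 - mean/variance, the standard error of the change contrast is too large by about sqrt(mean / [variance × (1 - r)]).

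Under the assumed values the loss runs from none to severe: over r = 0.80 to 0.90 at mean 9, a contrast with 80% true power keeps between 80% and 18%. The algebra and the simulation agree on the mechanism. Where this trial falls in that range cannot be settled from the documents.

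The consequence is limited to a possible missed effect on one primary outcome. It is worth acting on because the remedy costs almost nothing and can be fixed before the medication data are seen.

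**What to change.** For unique medications, state in the SAP that the group-by-time ratio will be estimated with a log-link count model on one pre and one post record per participant, and that tests and confidence intervals will use participant-clustered robust (sandwich) standard errors in place of the model-based negative binomial ones.

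This keeps the ratio as the effect measure and is valid whether the counts vary less or more than the model assumes, so no preliminary dispersion test is needed. A linear model for the count is not a substitute here, because it would change the effect from a ratio to a difference.

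The cost is one or two sentences in the SAP. With thousands of participants (the smallest collapsed group planned is 3 × 550 = 1,650), the robust errors should lose essentially nothing when the counts are not under-dispersed. In the simulation at the threshold correlation, with 2,200 per group, power was 0.81 with them and 0.79 without.

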GENERAL INFORMATION

Evaluation of a Letter Intervention Among At-risk Adults Promoting a Plant-based Diet Using a Combination of Provider Testimonials, the Forks Over Knives Documentary, and Commitment- or Prevention-focused Behavioral Nudges

[name].

[contact]

March 25, 2022

Version 1.1

OBJECTIVES

Our mission is to promote healthier eating behavior and to reduce costs associated with healthcare. The purpose of this study is to evaluate the effects of mailing randomly selected participants a letter promoting a plant-based diet. Depending on the experimental condition, participants may additionally receive a free documentary, Forks Over Knives, and they may also get letters which use commitment- or prevention-focused messages to encourage watching the documentary and changing their eating behavior. We hypothesize that receiving the documentary will be associated with lower insurance claims and improved health outcomes one and two years later. We also hypothesize that using either commitment- or prevention-focused messages will also contribute to lower insurance claims and improved health outcomes compared to experimental conditions where materials did not include these messages.

BACKGROUND AND RATIONALE

Heart disease and diabetes are the first and seventh leading causes of death in the United States, respectively (Xu J, Murphy SL, Kochanek KD, 2016). Further, these medical conditions put a large strain on the economy. In 2016, treating cardiovascular disease in the United States costed \$555 billion, while in 2017, diabetes contributed to \$327 billion in medical costs and reduced productivity (American Diabetes Association, 2018; American Heart Association, 2017).

To address these problems in a cost-effective way, multiple randomized control trials have provided evidence that interventions that change people's lifestyles can reduce the risk of heart disease and diabetes (for reviews, see Artinian et al., 2010; Dunkley et al., 2014; Wing et al., 2001). Many of these interventions involved structured programs such as diet and exercise schedules, group sessions, and individual counseling. These programs are still costly in terms of time and personnel commitment and may be difficult to scale up to a larger population. We aim to test whether simply sending people a letter and some materials promoting a healthy diet can by itself promote behavior change and improved health outcomes.

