Question 1: Does getting Forks Over Knives materials lead to improved outcomes over controls?

Passive Control	Active Control (Letter with no Video)	Letter with Video			
		Link	DVD	DVD + Link	
2200	2200	550	550	550	Letter Only
		550	550	550	Commitment Nudge
		550	550	550	Prevention Nudge
		550	550	550	Commitment + Prevention
2200	2200	2200	2200	2200	

Data for all participants who received Forks Over Knives materials (in yellow above) will be collapsed into one group.

Main analysis 1: Active Control, Passive Control vs. Forks Over Knives (reference group)

Exploratory analysis 1: Active Control vs. Passive Control (reference group)

Question 2: Do the behavioral science-informed components in the letter lead to improved outcomes over the controls?

Passive Control	Active Control (Letter with no Video)	Letter with Video			
		Link	DVD	DVD + Link	
2200	2200	550	550	550	Letter Only
		550	550	550	Commitment Nudge
		550	550	550	Prevention Nudge
		550	550	550	Commitment + Prevention
2200	2200	2200	2200	2200	

Data for all participants within each behavioral nudge condition (in yellow, green, grey, and white above) will be collapsed into one group.

Main analysis 2: Commitment Nudge, Prevention Nudge, Commitment + Prevention vs. Letter Only (reference group)

Main analysis 3: Commitment Nudge, Prevention Nudge, Commitment + Prevention, Letter Only vs. Active Control (reference group)

Main analysis 4: Commitment Nudge, Prevention Nudge, Commitment + Prevention, Letter Only vs. Passive Control (reference group)

Exploratory analysis 2: Commitment Nudge, Prevention Nudge vs. Commitment + Prevention (reference group)

Exploratory analysis 3: Commitment Nudge vs. Prevention Nudge (reference group)

Question 3: Does medium (DVD, Link, DVD + Link) influence outcomes?

Passive Control	Active Control (Letter with no Video)	Letter with Video			
		Link	DVD	DVD + Link	
2200	2200	550	550	550	Letter Only
		550	550	550	Commitment Nudge
		550	550	550	Prevention Nudge

		550	550	550	Commitment + Prevention
2200	2200	2200	2200	2200	

Data for all participants within each medium condition (in yellow, green, and grey above) will be collapsed into one group.

Exploratory analysis 4: DVD, Link, DVD + Link vs. Active Control (reference group)

Exploratory analysis 5: DVD, Link, DVD + Link vs. Passive Control (reference group)

Exploratory analysis 6: DVD, Link vs. DVD + Link (reference group)

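### SAP Question 2 names only row-versus-row nudge contrasts; prespecifying the commitment and prevention main effects and their interaction would halve the variance for each nudge's average effect

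*SAP*

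**What the plan says.** - Protocol, Research Design: "We will use an experimental study with a factorial design", set out as "14 groups: 1 control, 1 letter only, 3 methods of documentary distribution x 4 behavioral nudges". The nudge factor is written as four levels and is not called a 2x2.
- Protocol, Detailed Study Procedures: "Groups 3-14 (550 households each"), which receive the documentary and differ by delivery method and by nudge.
- SAP, Planned Analyses table: the four nudge rows are Letter Only, Commitment Nudge, Prevention Nudge and Commitment + Prevention. Letter Only here means the video letter with no nudge. It is not the protocol's letter group without the documentary, which the SAP calls Active Control.
- SAP, Question 2: the delivery methods are pooled within each row ("Data for all participants within each behavioral nudge condition"). The main comparison within the video groups is "Main analysis 2: Commitment Nudge, Prevention Nudge, Commitment + Prevention vs. Letter Only (reference group"). Comparisons with the controls follow, for example "Main analysis 3: Commitment Nudge, Prevention Nudge, Commitment + Prevention, Letter Only vs. Active Control (reference group"), and Main analysis 4 does the same against Passive Control. The combined row meets the single-nudge rows only in "Exploratory analysis 2: Commitment Nudge, Prevention Nudge vs. Commitment + Prevention (reference group").
- Protocol, Objectives: the nudge hypothesis is that either type of message helps "compared to experimental conditions where materials did not include these messages".

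**The concern.** A 2x2 lets every household inform both factors. The effect of commitment can be read from the rows without prevention and again from the rows with it, and the two readings averaged. Question 2 names neither that average nor the difference between the two readings (the interaction).

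Two things are at stake. The first is precision: Main analysis 2 has the largest standard error of the main analyses, although the same data would support a smaller one. The second is clarity: the plan does not say whether a nudge effect means its effect when used alone or its effect averaged over the other nudge. If that is left open until results are seen, a marginal or interaction contrast added later would be post hoc, and the choice between summaries would be open to selection.

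**Working it through.** **Inputs.** Cell size is 550 (protocol, Detailed Study Procedures; SAP table). The documents give no SD, alpha, sidedness or power for the nudge contrasts. I assume two-sided 0.05, 80% power, a common SD and equal rows, and work in SD units. These are planned sizes, before the SAP's exclusion of returned mail.

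**The plan's own figures.** The allocation reproduces: 6,200 + 2,200 + 12 x 550 = 15,000, and 2,200 + 6,600 = 8,800 mailed. The SAP table gives 5 x 2,200 = 11,000. The protocol's minimum of 400 households cannot be reproduced, because its effect size, SD, alpha, power and basis (per group or total) are not given. It also concerns book requesters, not nudges.

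**Step 1: row sizes.** Each row is 3 x 550 = 1,650, and the four rows total 6,600. Write L, C, P and CP for the means of Letter Only, Commitment, Prevention and Commitment + Prevention.

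**Step 2: the planned coefficient, for example C - L.**
- SE = sqrt(1/1650 + 1/1650) = 0.0348 SD.
- It rests on 3,300 of 6,600 video households (50%).

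**Step 3: the marginal contrast, [(C - L) + (CP - P)]/2.**
- SE = sqrt(4/1650)/2 = sqrt(2/3300) = 0.0246 SD, using all 6,600.
- SE ratio = 0.0246/0.0348 = 0.707, so the variance is halved. The ratio does not depend on SD, alpha or power.

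**Step 4: detectable difference and power.** The multiplier is 1.960 + 0.842 = 2.802.

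| Contrast | Households | SE (SD) | Detectable at 80% | Power at 0.05 SD | 0.07 SD | 0.10 SD |
|---|---|---|---|---|---|---|
| Single nudge vs Letter Only | 1,650 vs 1,650 | 0.0348 | 0.0975 | 30% | 52% | 82% |
| Nudge present vs absent | 3,300 vs 3,300 | 0.0246 | 0.069 | 53% | 81% | 98% |

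The power columns assume additivity, so that both contrasts estimate the same effect. The effect sizes are illustrative; the documents give none for a nudge.

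**Step 5: the other main analyses, SAP sizes.** Main analysis 1, 2,200 vs 6,600: sqrt(1/2200 + 1/6600) = 0.0246. Main analyses 3 and 4, 1,650 vs 2,200: sqrt(1/1650 + 1/2200) = 0.0326. Main analysis 2, at 0.0348, is the least precise. The margin would match Main analysis 1.

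**Step 6: the interaction, CP - C - P + L.** SE = sqrt(4/1650) = 0.0492 SD; detectable 2.802 x 0.0492 = 0.138 SD.

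**Step 7: when the gain disappears.** Let each nudge alone have effect d, and let the combined letter fall short of 2d by xd.
- The marginal effect is [d + d(1 - x)]/2 = d(1 - x/2).
- The power advantage is gone when 1 - x/2 = 0.707, that is x = 0.586.
- At x = 1 (the combined letter is no better than one nudge) and d = 0.07, the margin is 0.035 SD with about 30% power, against 52% for the simple contrast. At d = 0.10 it is 53% against 82%.
- In the first of those cases the interaction is 0.07 SD. Its power is also about 30% (0.07/0.0492 = 1.42), so it would usually miss the problem.

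**The case against.** The case for leaving Question 2 alone is substantial, and most of it stands.

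- **The simple effects are legitimate.** Comparing each nudge with a no-nudge letter does not assume additivity. Both nudges aim at getting people to watch the documentary, so overlap is plausible, and Step 7 shows that the margin can then be the weaker test. This stands. It is why the simple effects should keep their place.
- **The information is already there.** Main analysis 2 gives each nudge's effect without the other; Exploratory analysis 2 gives, with sign reversed, its effect in the other's presence. Margin and interaction are linear combinations of these. That is true, but neither is named, and one ingredient is labelled exploratory.
- **A reader might infer that the protocol's hypothesis goes untested.** The documents do not support that. The comparator wording, "compared to experimental conditions where materials did not include these messages", can mean letters with neither message, and Main analysis 2 uses exactly that row as its reference. It can also mean each message absent in turn, which no listed analysis tests. The sentence is ambiguous.
- **A reader might infer that half of all randomised households go unused.** They do not. The 50% applies to the 6,600 video households and to one coefficient at a time. All four rows enter Main analysis 2 and return in Main analyses 3 and 4.
- **Intent.** No passage says that the nudges were crossed to gain efficiency. The protocol attributes group sizes to a power analysis of book requesters and to the budget. The 2x2 is a fact of the four rows, not a stated aim.

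The SAP also does not say whether Main analysis 2 is three coefficients, a joint test or a pooled contrast. Pooled as any nudge versus none (4,950 vs 1,650), the SE is 0.0284 SD and the detectable difference 0.080 SD, with all 6,600 used. The efficiency figures above assume three coefficients.

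**Conclusion.** The concern holds as a loss of efficiency and an unstated estimand in a main analysis. Nothing planned is invalid or biased.

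The firm part is the SE ratio of 0.707 for the average effect of each nudge, which needs only equal rows and a common variance. The detectable differences (0.069 against 0.0975 SD) also rest on the assumed two-sided 0.05 and 80% power. The power gain at 0.07 SD (81% against 52%) needs additivity as well, and with equal nudge effects it vanishes once the combined letter falls short by about 59% of one nudge's effect. For costs and counts, which the SAP models with a log link, additivity means effects that multiply, and SD units are only a guide.

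The change is worth making because it is cheap, and because Secondary Analysis 2 reuses the same questions and would carry the gap forward.

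**What to change.** In SAP Question 2, Main analysis 2:

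1. Keep the three contrasts against Letter Only, and state that they are three separate contrasts if that is the intention.
2. From the same model of the 12 video groups, adjusted for medium, add the commitment margin [(C - L) + (CP - P)]/2 and the prevention margin [(P - L) + (CP - C)]/2.
3. Add the interaction CP - C - P + L with its confidence interval.
4. Report margins, interaction and simple effects together. Do not use the interaction test to choose between them, and do not demote the simple effects.
5. State which nudge effect the hypothesis refers to: against letters with neither message, or each message present versus absent.

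The cost is SAP wording and three more contrasts per outcome, with no new data. The extra contrasts should be counted in any multiplicity allowance, and the report should say that the margin is diluted if the nudges overlap. The SAP states that the data were unexamined when it was posted. If that still holds, the additions count as prespecified; if not, they should be labelled post hoc.
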